12.9.1.5. Dataset Specification

General description and rules:

- Missing or unknown values in covariates, if not to be imputed, will be assigned -99.
- The dataset is sorted by STUD, SUBJID, DATE, CTIM, EVID descending.
- The data items (columns) in the analysis-ready data file will be provided the same order as follows.
- Non-quantifiable (NQ) concentration values will be included as detailed for the CONC variable.
- Non-numerical concentration values (such as NS, NR, NA) will not be included.
- Placebo subjects will not be included.
- The dataset will be a comma delimited ASCII text file and will be named:
 - *NM.compound.study.PK.v1.csv*
 - Where “compound” is the compound name (e.g. GSK1234567) and “study” is the study number (e.g. 207551).

Variable	Label (Variable description)	Type	Units	Missing value	Codes/Derivation/Notes
ID	NONMEM subject identifier	Integer	None	Never	Sequential subject identifier across study after data is sorted by STUD, SUBJID, DATE, RTFD, EVID. Numbering to start at 1. To be entered in all rows for each subject.
STUDYID	Unique identifier for a study	Char	None	Never	207551 for all records
STUD	Study ID	Num	None	Never	207551 for all records
SUBJID	Subject identifier for study	Char	None	Never	Subject identifier, which must be unique within the study. The identification number of the subject as recorded on the CRF. Exclude placebo subjects. Include subjects who have received IP and have at least one measureable drug concentration. To be entered in all rows for each subject.
COUNTRY	Country	Char	None	Never	Country of the investigational site in which the subject participated in the trial; e.g. USA. To be entered in all rows for each subject.
SITEID	Unique identifier for a study site	Num	None	Never	e.g. PPD any lead zero should not be included. To be entered in all rows for each subject.
CONC	Drug Concentration	Num	ng/mL	Never	CONC=0 for PK_GSK1325756 records. No sample (NS), insufficient sample (IS) and no result (NR) records will be excluded from dataset. CONC='.' for PK_GSK1325756 records < LOQ (i.e. if drug conc is NQ).
LNCONC	Natural log of CONC column	Num	ng/mL	Never	Natural log of CONC column. If CONC=0, then LNCONC='.'.
LLQ	Lower Limit of quantification	Num	ng/mL	Never	LLQ=5 or from source data if different. To be entered in all rows for each

Variable	Label (Variable description)	Type	Units	Missing value	Codes/Derivation/Notes
					subject.

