LNLLQ	Natural log of LLQ column	Num	ng/mL	Never	Natural log of LLQ column. If LLQ=0, then LNLLQ='.'.
MATRIX	Sample matrix	Num	None	Never	MATRIX=1 (blood).
MATRTEXT	Sample matrix text	Char	None	Never	Text corresponding to code for MATRIX. Enter 'Blood' for all rows.
LABL	Label describing the record	Char	None	Never	LABL explains the type of measurement for CONC for the current record. LABL=DOSE_GSK1325756 for dose record. LABL=PK_GSK1325756 for blood concentration record.
DATE	Date of Record	MM/DD/YYYY	None	Never	Date of record.
DATETIME	Date and time of record	MM/DD/YYYY HH:MM:SS	None	Never	Date and time of record.
DAY	Study day number of record	Num	None	Never	Day of study relative to first IP dose.
NDAY	Nominal day	Num	day	Never	Schedule visit day of study relative to first IP dose.
NOMT	Nominal time since FIRST IP dose	Num	h	Never	Nominal time of study relative to first IP dose. NOMT=0 for first dosing record only.
NOMTLD	Nominal time since LAST IP dose prior to sample	Num	h	Never	Nominal time of study relative to last IP dose prior to sample. NOMTLD=0 for dosing records.
RTFD	Relative time from FIRST IP dose to current sample time	Num	h	Never	Actual time from FIRST dose of IP.
RTLTD	Relative time from LAST IP dose prior to sample	Num	h	Never	Actual time from last dose of IP prior to sample. When LABL=DOSE_GSK1325756, RTLTD=0. For pre-dose PK sample on Day 7, RTLTD is relative to the previous dose.
DOSE	Dose amount	Num	mg	Never	DOSE=35. To be entered in all rows for each subject.

Variable	Label (Variable description)	Type	Units	Missing value	Codes/Derivation/Notes
DRUG	Name of drug	Char	None	Never	DRUG=GSK1325756. To be entered in all rows for each subject.
REG	Dosing Regimen	Integer	None	Never	REG=2 for BD. To be entered in all rows for each subject.
REGTEXT	Subject dose regimen text	Char	None	Never	REGTXT=BD, text corresponding to code for REG. To be entered in all rows for each subject.
ROUT	Route of administration	Integer	None	Never	ROUT=1 for PO. To be entered in all rows for each subject.
ROUTTEXT	Subject route of administration text	Char	None	Never	ROUTTEXT=PO, text corresponding to code for ROUT. To be entered in all rows for each subject.
CMT	NONMEM Compartment code	Integer	None	Never	CMT=1 for DOSE_GSK1325756 records. CMT=2 for PK_GSK1325756 records.
EVID	NONMEM Event ID	Integer	None	Never	EVID=1 for LABL= DOSE_GSK1325756. EVID=0 for LABL= PK_GSK1325756.

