AMT	NONMEM Amount of drug administered	Num	mg	Never	AMT=0 for LABL= PK_GSK1325756 records. AMT=35 for LABL= DOSE_GSK1325756 records.
II	NONMEM Inter-dose interval	Integer	h	Never	II=0 for LABL= PK_GSK1325756. II=12 for LABL= DOSE_GSK1325756, except II=0 for LABL= DOSE_GSK1325756 on Day 1 only.
SS	Steady-state data item	Integer	None	Never	SS=0 for LABL= PK_GSK1325756 records. SS=1 for LABL= DOSE_GSK1325756 records, except SS=0 for LABL= DOSE_GSK1325756 records on Day 1 only.
RATE	NONMEM Rate of drug infusion	Integer	None	Never	RATE=0 for LABL= PK_GSK1325756 records. RATE=-2 for LABL= DOSE_GSK1325756 records.

Variable	Label (Variable description)	Type	Units	Missing value	Codes/Derivation/Notes
MDV	NONMEM Missing data value	Integer	None	Never	MDV=1 for LABL=DOSE_GSK1325756 records. MDV=0 for LABL=PK_GSK1325756 records. MDV=1 for LABL=PK_GSK1325756 records < LOQ (NQ).
VIS	Visit number	Integer	None	Never	From source data.
POP	Population	Integer	None	Never	POP=1, for COPD. To be entered in all rows for each subject.
POPTXT	Subject population text	Char	None	Never	POPTXT=COPD, text corresponding to code for POP. To be entered in all rows for each subject.
COH	Cohort	Integer	None	Never	COH=1. To be entered in all rows for each subject.
AGE	Subject Age	Integer	year	If missing impute with -99	From source data. To be entered in all rows for each subject.
SEX	Subject gender	Integer	None	Never	0=Male, 1=Female To be entered in all rows for each subject.
SEXTEXT	Subject gender text	Char	None	Never	Text corresponding to code for SEX, e.g. MALE or FEMALE). To be entered in all rows for each subject.
BMI	Baseline Body Mass Index	Num	kg/m ²	If missing impute with -99	Ensure consistent with S&P formula. E.g. Formula: Weight(kg)/(height(m)**2) To be entered in all rows for each subject.
BSA	Baseline Body Surface Area	Num	m ²	If missing impute with -99	Formula: BSA (m ²) = 0.024265 • Height(cm) ^{0.3964} • Weight(kg) ^{0.5378} Ensure consistent to with S&P formula. To be entered in all rows for each subject.
WT	Baseline Subject weight	Num	kg	If missing impute with -99	From source data. To be entered in all rows for each subject.
HT	Baseline Subject height	Num	m	If missing impute with -99	From source data. To be entered in all rows for each subject.
RACE1	Subject race code1	Integer	None	Never	From source data e.g. 1=African American / African

Variable	Label (Variable description)	Type	Units	Missing value	Codes/Derivation/Notes

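### The PopPK dataset specification sets CONC to 0 on the blood-concentration records instead of the dose records; a one-line label correction is needed (minor)

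*SAP*

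**What the plan says.** SAP Section 10 states that a PopPK dataset will be generated to support a population model that may be run. Section 12.9.1.5 gives the derivation rule for each variable. The rows that bear on this point are:

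- **CONC** (drug concentration, ng/mL): "CONC=0 for PK_GSK1325756 records". Records with no sample, insufficient sample or no result are dropped. For samples below the limit of quantification: "CONC='.' for PK_GSK1325756 records < LOQ (i.e. if drug conc is NQ").
- **LNCONC**: the natural log of CONC, set to missing when CONC is zero ("If CONC=0, then LNCONC" is '.').
- **LABL**: "LABL=PK_GSK1325756 for blood concentration record" and "LABL=DOSE_GSK1325756 for dose record".
- **EVID**: "EVID=0 for LABL= PK_GSK1325756".
- **MDV**: "MDV=0 for LABL=PK_GSK1325756 records", with MDV=1 for dose records and for non-quantifiable PK records.
- **AMT**, as an example of a row that treats both labels: "AMT=0 for LABL= PK_GSK1325756 records", and 35 for dose records.

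The missing-value column reads Never for both CONC and LNCONC.

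**The concern.** Read with the LABL row, the CONC rule zeroes exactly the records that should hold the measurement, and it gives dose records no value at all. A zero with EVID=0 and MDV=0 is not a blank: NONMEM would read it as an observed concentration of zero. SAP Section 10 and Protocol 10.3.3 both allow these data to be combined with historic data, so false zeros could be carried into a pooled fit. This is a derivation rule that a programmer executes and a second programmer checks against. A build that follows it would pass the check and still be wrong.

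**Working it through.** The plan states no figure to reproduce. The check is to apply the rules as written and then count the rows affected.

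**1. Scheduled samples per danirixin participant** (Protocol Section 2, footnotes 7 and 8; repeated in SAP 12.2.1)

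- Visit 2 (Day 1): pre-dose, 0.5, 1, 2 and 4 hours = 5
- Visit 3 (Day 7): pre-dose only = 1
- Visit 4 (Day 14): pre-dose, 0.5, 1, 2 and 4 hours = 5
- Total: 5 + 1 + 5 = 11

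The Day 1 pre-dose sample precedes any danirixin, so it is assumed non-quantifiable (NQ). That leaves 11 − 1 = 10 samples that can be quantifiable.

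**2. Rules applied to one illustrative participant.** There are 11 PK rows, with assumed concentrations on 10 and NQ on the Day 1 pre-dose row. The below-LOQ rule is read as an exception to the zero rule.

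| | As written | Zero moved to dose records, measured value on PK records |
|---|---|---|
| PK rows with a measured CONC | 0 of 11 | 10 of 11 |
| PK rows with CONC=0 | 10 | 0 |
| PK rows with CONC='.' | 1 | 1 |
| PK rows with a finite LNCONC | 0 | 10 |
| PK rows with MDV=0 | 10 | 10 |
| CONC on dose rows | undefined | 0 |

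As written, the 10 rows flagged as observations are the 10 false zeros. After the correction, they are the 10 rows with a measured value. The result of zero measured values does not depend on the concentrations assumed.

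**3. Scale**

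- Planned danirixin arm of 18 (Protocol synopsis; SAP 2.3): 10 × 18 = 180 records.
- SAP 3.2 reports an early stop with 19 completers. If 3:1 allocation held among them (an assumption), 19 × 3/4 = 14.25, so about 14 on danirixin and 10 × 14 = 140 records.

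**4. Is it a slip or a convention?** Other rules in the same specification make sense only if PK records hold measurements:

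- NQ values have their own exception. As written, unquantifiable samples would be missing while quantifiable ones would be zero.
- MDV separates quantifiable from NQ PK records.
- A participant needs at least one measurable concentration to enter the file.
- CMT, EVID, AMT, II, SS, RATE and MDV each give a rule for both PK and DOSE labels. CONC names only PK.

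The zero rule and its LNCONC companion both fit dose records. A PK/DOSE label slip is the natural explanation.

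**The case against.** The strongest reply is that little depends on this file and that the intent is recoverable. SAP 2.1 replaced the model-based endpoint (clearance, volume) with concentrations and AUC, Cmax and tmax, because few participants had PK data. Those parameters come from non-compartmental analysis (SAP 9.1.1.2) through a separate WinNonlin file (SAP 12.5.3). The PK tables, figures and listings (SAP 12.11.8, 12.11.9, 12.11.11) are not specified to draw on the NONMEM dataset. The population model is optional, has its own analysis plan and is reported outside the main study report. A literal build would leave LNCONC empty on every PK row, which is hard to miss. The measured values stay in the source data and the concentration listing, so the file can be regenerated.

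All of this stands, and it limits the consequence. It does not make the rule correct: the specification nowhere states what CONC should be on a quantifiable record.

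A reader might infer that the trial's PK objective would fail, since SAP 2.2 still words the objective as a population PK profile. The documents do not support that, because the endpoint now listed against the objective is the non-compartmental one. A reader might also count all 11 samples and report 11 × 18 = 198 zeroed records. That includes the Day 1 pre-dose sample, which is expected to fall under the missing-value rule and not the zero rule.

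**Conclusion.** The rule is wrong as written, and the point is minor. Built to specification, the PopPK dataset would hold no measured danirixin concentration, only zeros marked as observations with LNCONC missing. The number of zeroed records is at most about 180 at the planned size, or about 140 on the 19 completers. These counts assume that every scheduled sample is taken, that the Day 1 pre-dose sample is NQ and every other sample quantifiable and, for the second figure, that the 3:1 ratio held.

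The effect is confined to the NONMEM file and to any population or pooled model built from it. The primary, secondary, safety and non-compartmental PK results are untouched. Text lost when the table was extracted cannot be wholly excluded, but the cell reads as complete sentences and the paired rules in neighbouring rows are intact.

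**What to change.** Reword the CONC row of SAP 12.9.1.5 to give three rules:

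- DOSE_GSK1325756 records: CONC is 0.
- Quantifiable PK_GSK1325756 records: CONC is the measured concentration in ng/mL.
- PK_GSK1325756 records below the limit of quantification: CONC is '.', as now. The MDV row already assigns 1 to these, so it needs no change.

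At the same time, change the Never entries in the missing-value column for CONC and LNCONC, which conflict with the '.' coding. If a file has already been built, confirm that its PK rows hold measured values. The cost is one line of specification plus two table cells, with no effect on trial conduct or on any other analysis.

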12.10. Appendix 10: Abbreviations & Trade Marks

12.10.1. Abbreviations

Abbreviation	Description
ADaM	Analysis Data Model
AE	Adverse Event
AIC	Akaike's Information Criteria
A&R	Analysis and Reporting
CDISC	Clinical Data Interchange Standards Consortium
CI	Confidence Interval
CPMS	Clinical Pharmacology Modelling & Simulation
CS	Clinical Statistics
CSR	Clinical Study Report
CTR	Clinical Trial Register
CV _b / CV _w	Coefficient of Variation (Between) / Coefficient of Variation (Within)
DBF	Database Freeze
DBR	Database Release
DOB	Date of Birth
DP	Decimal Places
eCRF	Electronic Case Record Form
EMA	European Medicines Agency
FDA	Food and Drug Administration
FDAAA	Food and Drug Administration Clinical Results Disclosure Requirements
GSK	GlaxoSmithKline
IA	Interim Analysis
ICH	International Conference on Harmonization
IDMC	Independent Data Monitoring Committee
IDSL	Integrated Data Standards Library
IMMS	International Modules Management System
IP	Investigational Product
ITT	Intent-To-Treat
MMRM	Mixed Model Repeated Measures
mITT	Modified Intent to Treat
NETs	Neutrophil Extracellular Traps
PCI	Potential Clinical Importance
PD	Pharmacodynamic
PDMP	Protocol Deviation Management Plan
PK	Pharmacokinetic
PP	Per Protocol
PopPK	Population PK
QC	Quality Control
QTcF	Frederica's QT Interval Corrected for Heart Rate
QTcB	Bazett's QT Interval Corrected for Heart Rate
RAP	Reporting & Analysis Plan
RAMOS	Randomization & Medication Ordering System

Abbreviation	Description
SAC	Statistical Analysis Complete
SDSP	Study Data Standardization Plan
SDTM	Study Data Tabulation Model
SOP	Standard Operation Procedure
TA	Therapeutic Area
TFL	Tables, Figures & Listings

12.10.2. Trademarks

Trademarks of the GlaxoSmithKline Group of Companies
None

Trademarks not owned by the GlaxoSmithKline Group of Companies
WinNonlin
SAS

12.11. Appendix 11: List of Data Displays

12.11.1. Data Display Numbering

The following numbering will be applied for RAP generated displays:

Section	Tables	Figures
Study Population	1.1 to 1.21	
Efficacy	2.1 to 2.22	2.1 to 2.18
Safety	3.1 to 3.14	
Pharmacokinetic	4.1 to 4.2	4.1 to 4.6
Section	Listings	
ICH Listings	1 to 30	
Other Listings	31 to 44	

12.11.2. Mock Example Shell Referencing

Non IDSL specifications will be referenced by the name of the table or figure and if required example mock-up displays provided in [Appendix 12: Example Mock Shells for Data Displays](#).

12.11.3. Deliverables

Delivery [Priority] ^[1]	Description
SAC [X]	Final Statistical Analysis Complete
D	Will be part of the abbreviated dry run

NOTES:

1. Indicates priority (i.e. order) in which displays will be generated for the reporting effort

12.11.4. Study Population Tables

Study Population Tables					
No.	Population	IDSL / Example Shell	Title	Programming Notes	Deliverable [Priority]
Subject Disposition					
1.1.	mITT	ES1	Summary of Subject Disposition for the Subject Conclusion Record	ICH E3, FDAAA, EudraCT, Use latest screening	SAC [2]
1.2.	mITT	SD1	Summary of Treatment Status and Reasons for Discontinuation of Study Treatment	ICH E3	SAC [2]
1.3.	Enrolled	ES6	Summary of Screening Status and Reasons for Screen Failure	Journal Requirements, Use latest screening. If a subject is rescreened only use final re-screen	SAC [2]
1.4.	Enrolled	NS1	Summary of Number of Subject by Country and Site ID	EudraCT/Clinical Operations	SAC [2]
1.5.	mITT	NS1	Summary of Number of Subject by Country and Site ID	EudraCT/Clinical Operations	SAC [2]
1.6.	Primary Completer	NS1	Summary of Number of Subject by Country and Site ID	EudraCT/Clinical Operations. If the primary completer and mITT population are the same do not recreate	SAC [2]
Protocol Deviation					
1.7.	mITT	DV1	Summary of Important Protocol Deviations	ICH E3	SAC [2]
1.8.	Enrolled	IE1	Summary of Inclusion/Exclusion Criteria Deviations for Screen or Run-in failures		SAC [2]
1.9.	mITT	IE1	Summary of Inclusion/Exclusion Criteria Deviations for the Modified Intent-to-treat Population		SAC [2]

Study Population Tables					
No.	Population	IDSL / Example Shell	Title	Programming Notes	Deliverable [Priority]
Population Analysed					
1.10.	Enrolled	SP1	Summary of Study Populations	IDSL Number of participants who were in the Enrolled population, who were randomized, the number in the mITT population. Of those in the mITT, the number and percentage of participants in the primary completer population	SAC [2]
Demographic and Baseline Characteristics					
1.11.	mITT	DM1	Summary of Demographic Characteristics	ICH E3, FDAAA, EudraCT	SAC [2]
1.12.	Primary Completer	DM1	Summary of Demographic Characteristics	ICH E3, FDAAA, EudraCT	SAC [2]
1.13.	Enrolled	DM11	Summary of Age Ranges	EudraCT	SAC [2]
1.14.	mITT	PD4	Summary of Screening and Baseline Spirometry Measures	Pre-BD FEV1 (L), Post-BD FEV1 (L), Predicted normal FEV1 (L), Percent predicted normal post-BD FEV1 (%), Percent predicted normal post-BD FEV1: <50%, >=50%, Post-BD FVC (L), Post-BD FEV1/FVC Footnote: Subjects are only supposed to have a Post Sputum Induction FEV1 at baseline if participant was unable to give a sample at Pre-Screening. The pre-screening and screening samples for this measure are combined.	SAC [2]
1.15.	mITT	SU1	Summary of Smoking History and Smoking Status at Screening	Include smoking status, smoking pack years, cigarettes smoked/day	SAC [2]
1.16.	mITT	DM6	Summary of Race and Racial Combinations	ICH E3, FDA, FDAAA, EudraCT	SAC [2]

Study Population Tables					
No.	Population	IDSL / Example Shell	Title	Programming Notes	Deliverable [Priority]
Prior and Concomitant Medications					
1.17.	mITT	MH4	Summary of Current Medical Conditions	ICH E3	SAC [2]
1.18.	mITT	MH4	Summary of Past Medical Conditions	ICH E3	SAC [2]
1.19.	mITT	CM1	Summary of Concomitant Medications	ICH E3	SAC [2]
1.20.	mITT	CM1	Summary of COPD Concomitant Medications Taken Pre-treatment		SAC [2]
1.21.	mITT	CM1	Summary of COPD Concomitant Medications Taken Post-treatment		SAC [2]

12.11.5. Efficacy Tables

Efficacy: Tables					
No.	Population	IDSL / Example Shell	Title	Programming Notes	Deliverable [Priority]
NETs					
2.1	Primary Completer		Summary of Adjusted Mean Change from Baseline of NETs Quantified by Histone-Elastase		D, SAC [2]
2.2	Primary Completer		Summary of Unadjusted Means of NETs	Histone, DNA, and microscopy quantified	D, SAC [1]
2.3	Modified Primary Completer		Summary of Unadjusted Means of NETs for the Modified Primary Population	Histone, DNA, and microscopy quantified. This population will only be use if this increases the available sample from the Primary completer population by 20%.	SAC [2]
2.4	Primary Completer		Summary Unadjusted Mean Change from Baseline of NETs	Include percent change from baseline	D, SAC [2]
2.5	Primary Completer		Summary of the Ratio of Sputum NETs to Sputum Neutrophils		D, SAC [2]
2.6	Primary Completer		Summary of Change from Baseline in the Ratio of Sputum NETs to Sputum Neutrophils		D, SAC [2]
2.7	Primary Completer		Summary of Sputum Neutrophils		D, SAC [1]
2.8	Primary Completer		Summary of Change from Baseline in Sputum Neutrophils		D, SAC [2]
2.9	mITT		Summary of Peripheral Blood Neutrophil NETs Formation	Will be measured by DNA release and microscopy, summarise no PMA and PMA values septately, but include both on the table. Only collected at baseline and day 14	D, SAC [1]

Efficacy: Tables					
No.	Population	IDSL / Example Shell	Title	Programming Notes	Deliverable [Priority]
2.10	mITT		Summary of Change from Baseline in Peripheral Blood Neutrophil NETs Formation	Will be measured by DNA release and Microscopy	D, SAC [2]
2.11	mITT		Summary of Sputum Quality	Number of subjects with Insufficient Tissue, Poor Quality, Acceptable, and Good Quality samples see MISPQL variable for quality flag Mean and SD of Squamous epithelial cells. Mean and SD of Viable Leukocytes.	D, SAC [2]
2.12	Primary Completer		Summary of Sputum Quality	Number of subjects with Insufficient Tissue, Poor Quality, Acceptable, and Good Quality samples see MISPQL variable for quality flag Mean and SD of Squamous epithelial cells. Mean and SD of Viable Leukocytes .	D, SAC [2]
CAT					
2.13	mITT		Summary of Baseline CAT		SAC [2]
Biomarker					
2.14	Primary Completer		Summary of Change from Baseline Sputum Resistin Levels		D, SAC [2]
2.15	Primary Completer		Summary of Sputum Resistin Levels		D, SAC [2]
2.16	Primary Completer		Summary of Change from Baseline in Sputum Elastase Activity		D, SAC [2]
2.17	Primary Completer		Summary of Sputum Elastase Activity		D, SAC [2]

Efficacy: Tables					
No.	Population	IDSL / Example Shell	Title	Programming Notes	Deliverable [Priority]
2.18	mITT		Summary of Change from Baseline in Ex-Vivo Neutrophil Phagocytosis of Bacteria by Flow Cytometry		D, SAC [2]
2.19	mITT		Summary of Ex-Vivo Neutrophil Phagocytosis of Bacteria by Flow Cytometry		D, SAC [2]
2.20	mITT		Summary of Change from Baseline of Blood Biomarkers	Include plasma fibrinogen and serum C-reactive protein. For values below the LLQ use X/2	D, SAC [2]
2.21	mITT		Summary of Blood Biomarkers	Include plasma fibrinogen and serum C-reactive protein. For values below the LLQ use X/2	D, SAC [2]
Exploratory					
2.22	mITT		Summary of VOCs Variability		SAC [2]

12.11.6. Efficacy Figures

Efficacy: Figures					
No.	Population	IDSL / Example Shell	Title	Programming Notes	Deliverable [Priority]
NETs					
2.1	Primary Completer		Adjusted Mean (95% CI) Change from Baseline of NETs Quantified by Histone-Elastase		D, SAC [2]
2.2	Primary Completer		Unadjusted Mean and (95% CI) Change from Baseline of NETs Quantified by Histone-Elastase, DNA-Elastase, and Microscopy	Please add text below indicating the number of subjects in each quality category. Percentage change.	D, SAC [2]

Efficacy: Figures					
No.	Population	IDSL / Example Shell	Title	Programming Notes	Deliverable [Priority]
2.3	Modified Primary Completer		Unadjusted Mean and (95% CI) Change from Baseline of NETs Quantified by Histone-Elastase, DNA-Elastase, and Microscopy for the Modified Primary Population	Please add text below indicating the number of subjects in each quality category. Percentage change. This population will only be use if this increases the available sample from the Primary completer population by 20%.	SAC [2]
2.4	Primary Completer		Spaghetti Plot of Change from Baseline of NETs		D, SAC [2]
2.5	Primary Completer		Spaghetti Plot of NETs		D, SAC [2]
2.6	Modified Primary Completer		Spaghetti Plot of NETs for the Modified Primary Population	This population will only be use if this increases the available sample from the Primary completer population by 20%.	SAC [2]
2.7	Primary Completers		Spaghetti and Boxplot of Baseline and Day 14 of NETs Quantified by Histone Elastase		D, SAC [2]
2.8	Primary Completers		Spaghetti and Boxplot of Baseline and Day 14 of Neutrophils		D, SAC [2]
2.9	mITT		Spaghetti and Boxplot of Baseline and Day 14 of Peripheral Blood NETs	For no PMA values only. Will be measured by DNA release and microscopy	D, SAC [2]
2.10	Primary Completer		Spaghetti Plot of Change from Baseline in the Ratio of Sputum NETs to Sputum Neutrophils		D, SAC [2]
2.11	Primary Completer		Spaghetti Plot of Ratio of Sputum NETs to Sputum Neutrophils		D, SAC [2]

Efficacy: Figures					
No.	Population	IDSL / Example Shell	Title	Programming Notes	Deliverable [Priority]
2.12	mITT		Spaghetti Plot of Change from PMA in Peripheral Blood Neutrophil NETs Formation	Facet the plot by the change that occurs on day -1 and on day 14. Will be measure by DNA release and microscopy	D, SAC [2]
2.13	mITT		Spaghetti and Boxplot of Peripheral Blood Neutrophil NETs Formation		D, SAC [2]
2.14	mITT		Boxplot of Change from Baseline in Peripheral Blood Neutrophil NETs Formation	For Placebo and treatment	D, SAC [2]
2.15	Primary Completer		Spaghetti Plot of Change from Baseline of Sputum Neutrophils		D, SAC [2]
2.16	Primary Completer		Spaghetti Plot of Sputum Neutrophils		D, SAC [2]
Biomarkers					
2.17	mITT		Mean and (95% CI) of Change from Baseline in Ex-Vivo Neutrophil Phagocytosis of Bacteria by Flow Cytometry		SAC [2]
2.18	mITT		Mean and (95% CI) of Change from Baseline of Blood Biomarkers		SAC [2]

